 Yes  No	Relate to cancer patients, cancer treatments, cancer screening/prevention, or tobacco?	Complete the CPRC application process. Contact: [contact]	
 Yes  No	Include the use of radiation? (x-ray imaging, radiopharmaceuticals, external beam or brachytherapy)	Complete the AURPC Human Use Application and follow instructions on the form for submission to the AURPC committee. Contact: [contact]	Approval from these committees must be received prior to IRB approval;
 Yes  No	Use the Center for Magnetic Resonance Research (CMRR) as a study location?	Complete the CMRR pre-IRB ancillary review Contact: [contact]	
 Yes  No	Include the use of recombinant or synthetic nucleic acids, toxins, or infectious agents?	Complete the IBC application via eprotocol.umn.edu Contact:	These groups each have their own application process.
 Yes  No	Include the use of human fetal tissue, human embryos, or embryonic stem cells?	Contact OBAO for submission instructions and guidance	

MEDICAL PROTOCOL (HRP-590)

PROTOCOL TITLE: Exercise and the Gut Microbiome R21

VERSION DATE: 05/11/2022

 Yes  No	Include PHI or are you requesting a HIPAA waiver?	If yes, HIPCO will conduct a review of this protocol. Contact: [contact]	
 Yes  No	Use data from the Information Exchange (IE)?	The Information Exchange ancillary review will be assigned to your study by IRB staff Contact: [contact]	Approval must be received prior to IRB approval.
 Yes  No	Use the Biorepository and Laboratory Services to collect tissue for research?	The BLS ancillary review will be assigned to your study by IRB staff. Contact: [contact]	These groups do not have a separate application process but additional information from the study team may be required.
 Yes  No	Have a PI or study team member with a conflict of interest?	The Col ancillary review will be assigned to your study by IRB staff Contact: [contact]	
 Yes  No	Need to be registered on clinicaltrials.gov?	If you select "No" in ETHOS, the clinicaltrials.gov ancillary review will be assigned to your study by IRB staff Contact: [contact]	
 Yes  No	Require registration in OnCore?	If you select "No" or "I Don't Know" in ETHOS, the OnCore ancillary review will be assigned to your study by IRB staff Contact: [contact]	Does not affect IRB approval.

MEDICAL PROTOCOL (HRP-590)

PROTOCOL TITLE: Exercise and the Gut Microbiome R21

VERSION DATE: 05/11/2022

REVISION HISTORY

Revision #	Version Date	Summary of Changes	Consent Change?
1	3/25/2020	We have made changes to clarify two points. First, we ensured that the compensation listed for all documents is \$80. Second, we have clarified how the Physical Activity Readiness Questionnaire will be scored as it pertains to inclusion and exclusion (Sections 8.1 and 13.1). Notably, we have also better clarified scoring in the phone-based screening questionnaire to be used by the research team to screen participants for inclusion in the trial.	No.
2	4/14/2021	We have updated this protocol to reflect: (1) the precautions our research team will be taking to reduce the potential for SARS-CoV-2 transmission; (2) the methodology we will use to deliver this trial in a remote manner if/when in-person exercise sessions are not possible due to the COVID-19 pandemic and/or participant preference (Sections 4.1 and 5.2). Additionally, the protocol was edited for clarity and to avoid redundancies.	No.
3	05/25/2021	We have updated this protocol to reflect: 
 - The removal of waist circumference measures at the in-person visits - the removal of a fasting blood draw measure at week 4 - the removal of a study questionnaire at each assessment visit 	Yes. See updates dated 5-25-2021
4	07/21/2021	We have updated this protocol to specifically add ResearchMatch as a recruitment methodology (See Section 11.1). We have also re-considered our compensation amount and have made a nominal increase in amount (See Section 11.4).	Yes. See updates dates 7-21-2021.
5	09/08/2021	We removed the use of Proton-Pump Inhibitors as one of the exclusionary criteria (see section 8.2)	

MEDICAL PROTOCOL (HRP-590)

PROTOCOL TITLE: Exercise and the Gut Microbiome R21

VERSION DATE: 05/11/2022

Revision #	Version Date	Summary of Changes	Consent Change?

- **T2D: type 2 diabetes** - highly prevalent cardiometabolic disease that up to 70% of prediabetics will convert to if steps are not taken to impede this conversion.
- **QIIME, DADA2, phyloseq, DESeq2, and SAS**: software packages to be used in the proper analyses of all study data.

MEDICAL PROTOCOL (HRP-590)

PROTOCOL TITLE: Exercise and the Gut Microbiome R21

VERSION DATE: 05/11/2022

1.0 Objectives

1.1 **Purpose:** We propose a 100-participant randomized controlled 2-arm parallel trial which employs a metagenomic approach to examine how 8 weeks of supervised moderate-intensity treadmill walking exercise (MWE)^{1,2} for 30-45 min 3 times/week alters the gut microbiome, serum SCFAs, and the cardiometabolic profile, body weight, and body composition of individuals 30-64 years old who are overweight or obese and have PreD.

Aim 1: Compare the effect of 8 weeks of MWE vs. control on shifts in the gut microbiome of overweight or obese individuals with PreD. **H1:** Gut microbial diversity and functional capacity (specifically, genes relevant to SCFA production) will increase improve after 8 weeks in the experimental group vs. control.

Aim 2: Compare the effect of 8 weeks of MWE vs. control on changes in serum SCFAs. **H2:** Serum Levels of SCFAs butyrate, acetate, and propionate will increase after 8 weeks in the experimental group vs. control.

Aim 3: Use formal mediation methods to estimate the proportion of MWE-induced changes in participants' cardiometabolic profiles, body weight, and body composition that are mediated by changes in the gut microbiome and/or serum SCFAs. **H3:** MWE-induced changes in the gut microbiome and serum SCFAs will partly explain changes in participants' cardiometabolic profile (e.g., blood lipids, fasting insulin/glucose, blood pressure, waist circumference), body weight, and body composition.

2.0 Background

2.1 **Significance of Research Question/Purpose:** In the U.S, 91.8 million adults have prediabetes (PreD).³ The prediabetic state is a prominent public health problem as up to 70% of individuals with PreD convert to type 2 diabetes (T2D).⁴ The risk of cardiovascular disease (CVD) is high among those with PreD and T2D, and nearly \$330 billion/year is spent treating T2D.^{3,5-7} The *American Heart Association (AHA)* and *American Diabetes Association (ADA)* have thus called for continued investigation into mechanisms connecting health behaviors to pre-clinical cardiometabolic disease (CMD; e.g., PreD) to reduce future disease risk.^{8,9} Physical activity (PA) is a key modifiable determinant of good health.¹⁰ Literature suggests PA recommendation¹⁰ adherence is related to a 25-35% dose-dependent reduction in all-cause mortality^{1,11,12}, with as little as 75 min/week of regular moderate-intensity PA beneficial.¹ Data from the Diabetes Prevention Program (DPP) suggested that, among those with PreD, a behavioral intervention emphasizing PA and diet to be at least as successful as metformin in preventing T2D, partially due to weight loss during this

MEDICAL PROTOCOL (HRP-590)

PROTOCOL TITLE: Exercise and the Gut Microbiome R21

VERSION DATE: 05/11/2022

trial.¹³ Yet, many individuals do not fully realize the cardiometabolic benefits of PA, and mechanistic pathways linking PA and cardiometabolic improvements are not fully understood.^{8,9,14,15} The gut microbiome¹⁶ has been posited as a mechanistic intermediate linking health behaviors such as PA to CMD development.^{14,17-19}

The gut microbiome may be important for immunological,^{20,21} metabolic,^{16,22} inflammatory,^{18,23,24} and neurobehavioral processes^{22,24,25}, some of which might partially explain how health behaviors influence CMD risk. Yet, limited evidence exists characterizing the effect of PA on the human gut microbiome. To date, most studies of the impact of PA interventions on the gut microbiome have used animal models,²⁶⁻⁴¹ with these studies supporting regular chronic PA (i.e., exercise) as a modulator of the gut microbiota. Animal studies have most often reported exercise-related changes to the Firmicutes^{27-31,38} or Bacteroidetes^{26,34,35,40} phyla while also noting beneficial alterations to microbial community diversity^{26,29,30,32-35,38-40} and short chain fatty acid (SCFA)-producing taxa^{33-36,38,41}. SCFAs are reported to promote gastrointestinal health, increase energy expenditure⁴², and to be related to a lean phenotype.^{14,27,41} The five existing human gut microbiome trials⁴³⁻⁴⁷ most often implemented non-controlled studies of 5- to 8-weeks of moderate-intensity exercise on 3 days/week for 30-60 min/session. Among overweight or obese adults, prior studies⁴³⁻⁴⁵ note increased α -diversity and altered β -diversity as a result of exercise; similar findings emerged in another study of healthy older adults.⁴⁶ Additionally, one study noted exercise to result in increases in SCFAs (in stool), and corresponding changes to SCFA-related bacterial genes and taxa,⁴⁵ while two other studies observed improvements in the metabolic potential of the gut microbiome^{43,44}. These findings corroborate observational studies in humans wherein more physically active individuals have greater microbiota diversity and/or improved capacity to produce SCFAs than less active individuals.⁴⁸⁻⁵³ **To our knowledge, no randomized controlled parallel design study has been conducted using metagenomic profiling (i.e., assessments of microbial functional capacity) to examine the influence of exercise on the human gut microbiome and serum SCFA levels in a population with a pre-clinical CMD. Moreover, no study has tested if changes in these outcomes mediate changes in cardiometabolic profiles or body weight and composition.**

The proposed study is innovative for the following reasons. First, we know of no other study in individuals who are overweight or obese with PreD that has examined how an exercise program may modify the gut microbiome and serum SCFAs. Second, we will study, for the first time, the interrelationship between exercise and the gut metagenome using a recently validated method for 'shallow shotgun' sequencing.⁵⁴ The shallow shotgun approach enables interrogation of the gut metagenome at a cost

MEDICAL PROTOCOL (HRP-590)

PROTOCOL TITLE: Exercise and the Gut Microbiome R21

VERSION DATE: 05/11/2022

that scales to longitudinal repeated measures study designs. As such, we will generate novel data on longitudinal changes in the gut metagenome resulting from MWE in individuals with PreD via thorough examination of the function of various microbial taxa and their effect on health over time.⁵⁵ Finally, the use of formal mediation analyses to examine the degree to which MWE-related changes in the preceding outcomes mediate changes in cardiometabolic risk profiles is novel and will inform the relative importance of the gut microbiome in exercise-related cardiometabolic improvements. These mediation analyses will also allow for a deeper interpretation of the physiological mechanisms by which exercise promotes improved health—addressing calls by the AHA and ADA.^{8,9}.

- 2.2 **Preliminary Data:** To date, only five human trials have investigated the effect of exercise on the gut microbiome.⁴³⁻⁴⁷, with none of these studies having been conducted in a population with a subclinical CMD (e.g., PreD). Further, there are notable limitations to these human studies. First, aside from Kern et al.⁴³, no study employed a true control group. Second, most studies were conducted in small samples of apparently healthy adults, with only two studies^{44,47} incorporating a true metagenomic sequencing approach. Incorporating a metagenomic approach (i.e., assessing microbial genes and functional capacity) allows for a deeper understanding of microbial diversity and ecology as well as better elucidation of the function of various microbial taxa and their effect(s) on health.⁵⁵ Finally, Allen et al.⁴⁵ only assessed SCFAs changes in stool and not in serum.
- 2.3 **Existing Literature:** The gut microbiome¹⁶ has been posited as a mechanistic intermediate linking health behaviors such as PA to CMD development.^{14,17-19} The gut microbiome may be important for immunological,^{20,21} metabolic,^{16,22} inflammatory,^{18,23,24} and neurobehavioral processes^{22,24,25}, some of which might partially explain how health behaviors influence CMD risk. Yet, limited evidence exists characterizing the effect of PA on the human gut microbiome. To date, most studies of the impact of PA interventions on the gut microbiome have used animal models,²⁶⁻⁴¹ with these studies supporting regular chronic PA (i.e., exercise) as a modulator of the gut microbiota. Animal studies have most often reported exercise-related changes to the Firmicutes^{27-31,38} or Bacteroidetes^{26,34,35,40} phyla while also noting beneficial alterations to microbial community diversity^{26,29,30,32-35,38-40} and short chain fatty acid (SCFA)-producing taxa^{33-36,38,41}. SCFAs are reported to promote gastrointestinal health, increase energy expenditure⁴², and to be related to a lean phenotype.^{14,27,41} The five existing human gut microbiome trials⁴³⁻⁴⁷ most often implemented non-controlled studies of 5- to 8-weeks of moderate-intensity exercise on 3 days/week for 30-60 min/session. Among overweight or obese adults, prior studies⁴³⁻⁴⁵ note increased β -diversity and altered β -diversity as a result of exercise; similar findings emerged in

MEDICAL PROTOCOL (HRP-590)

PROTOCOL TITLE: Exercise and the Gut Microbiome R21

VERSION DATE: 05/11/2022

another study of healthy older adults.⁴⁶ Additionally, one study noted exercise to result in increases in SCFAs (in stool), and corresponding changes to SCFA-related bacterial genes and taxa,⁴⁵ while two other studies observed improvements in the metabolic potential of the gut microbiome^{43,44}. These findings corroborate observational studies in humans wherein more physically active individuals have greater microbiota diversity and/or improved capacity to produce SCFAs than less active individuals.⁴⁸⁻⁵³

3.0 Study Endpoints/Events/Outcomes

3.1 **Primary Endpoint/Event/Outcome:** Expanded data collection procedures for our primary and secondary outcomes are available in Section 5.2. We have two Primary Outcomes. The first primary outcome is changes to the gut microbiome, assessed via metagenomic sequencing, from pre- to post-intervention (**Specific Aim 1**). The Shannon Index—a measure of microbial community diversity with good reproducibility (ICCs>0.50)⁵⁶—will be our primary indicator for changes in gut microbiota composition, and will be assessed at baseline, and following the 4th and 8th weeks. The second primary outcome is serum SCFA levels. Participants will undergo fasted blood draws to assess serum SCFA levels (**Specific Aim 2**). This work will be performed using the Metabolon pipeline.⁵⁷

3.2 **Secondary Endpoint(s)/Event(s)/Outcome(s):** We have several Secondary Outcomes. For **Specific Aim 3** cardiometabolic profiles will be assessed via assays for high-density lipoprotein cholesterol (HDL-C), triglycerides, fasting insulin/glucose, and c-reactive protein (CRP). All blood assays will be conducted by the *UMN Advanced Research and Diagnostic Laboratory* (see ‘Facilities’ document). Blood samples collected will be stored at -80°C prior to batch-processing. Resting blood pressure (BP) will be taken using an Omron Automatic BP Cuff (Omron; Lake Forest, IL), with the average of the last two BP measurements reported. These cardiometabolic indices form the foundation of the ‘metabolic syndrome’,⁵⁹⁻⁶³ and we will form a composite continuous score for cardiometabolic disease risk from HDL-C, fasting glucose, triglycerides, the average of systolic and diastolic BP, and waist circumference. Specifically, z-scores for each biomarker will be calculated and the within-participant average across z-scores computed and referred to as *cardiometabolic disease risk (CMDrisk*; the primary dependent variable for Specific Aim 3). This score has been used in epidemiologic, experimental, and clinical studies.^{62,64-67} Individual components will be described in secondary analyses as needed. We will also measure HbA1c using whole blood analyzed at the UMN Advanced Research Diagnostic Laboratory; the A1cNOW+® device may also be used in a limited capacity to assess validity.⁶⁸ The oral microbiome will be

MEDICAL PROTOCOL (HRP-590)

PROTOCOL TITLE: Exercise and the Gut Microbiome R21

VERSION DATE: 05/11/2022

assessed using a widely employed salivary testing technique. Briefly, we will ask that participants chew a paraffin tablet (Orion Diagnostica) for 5 minutes after which the participant will be asked to spit into a 50mL tube until 5mL of saliva is collected. We have experience with this non-invasive assessment⁶⁹, with the assessment taking no longer than 5-10 minutes overall and presenting no greater than minimal risk. Other secondary outcomes are necessary to measure to ensure we can properly control for confounding. Dietary composition will be assessed via 3 phone-based dietary recalls during the run-in phase, and again during the final two weeks of the study. We will use these dietary recalls collected during the run-in period to develop personalized 3-day meal plan to standardize individual dietary behavior prior to stool sample collection. Employing dietary recalls at these time points will also allow us to adequately statistically control for participants' dietary changes—changes which, if not controlled, might confound study results.^{70,71} Physical activity will be measured for the duration of the study using the Fitbit Inspire 2 smartwatch that uses accelerometry to measure physical activity metrics such intensity, steps, etc. Finally, anthropometric outcomes will include height, weight, and body composition. These measures, along with the other secondary outcomes aside from PA and Dietary composition, will be measured at the end of the 3-week run-in phase, and at the end of the 4th and 8th study weeks.

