5.2 **Study Procedures:** All eligible and consented participants will complete a 3-week run-in phase during which baseline outcome assessments will be performed. During run-in weeks 1 and 2, participants will wear a Fitbit Inspire 2 smartwatch and complete three unannounced dietary recalls. During the run-in week 3 (see table below), participants will consume their 3-day standardized meal plan on days three through five, obtain a fecal sample, and complete a study assessment visit. To quantify compliance with the 3-day meal plan, participants will be provided with a paper checklist of all foods to be consumed, and will be asked to indicate which foods were consumed and to document any deviation. The study assessment visit will include a fasting blood draw, blood pressure in triplicate, weight measure and body fat assessment in duplicate, and a saliva sample. Following successful completion of all measures, participants will then be randomized into one of the two study groups using PROC PLAN (SAS 9.4) and a 1:1 allocation ratio.

Group 1 (Experimental group): Participants will complete 3 treadmill walking sessions/week (24 total sessions) over 8 weeks at or around their home or in-person within the Epidemiology Clinical Research Center. Each walking sessions will be 30 min in duration during intervention weeks 1

MEDICAL PROTOCOL (HRP-590)

PROTOCOL TITLE: Exercise and the Gut Microbiome R21

VERSION DATE: 05/11/2022

through 4 and 45 min during intervention weeks 5 through 8. Notably, this exercise dose (i.e., intensity x session duration x weekly frequency x intervention length) is equivalent to, or greater than, that employed in most existing human studies of exercise and the gut microbiome in addition to the exercise dosage observed necessary to yield meaningful cardiometabolic changes.⁷² Therefore, while the dose is 'modest', it reflects what is relevant in real-world interventions and appropriate for overweight or obese sedentary individuals.

During week 4, participants will again consume their 3-day standardized meal plan, obtain a fecal sample, and complete a study assessment visit (same measures as described above for the 3-week run-in, except no fasting blood draw will be taken).

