The second primary outcome is serum SCFA levels. Participants will undergo fasted blood draws to assess serum SCFA levels (**Specific Aim 2**). This work will be performed using the Metabolon pipeline.⁵⁷ Briefly, serum samples are spiked with a solution of eight stable labelled internal standards and subjected to protein precipitation. After centrifugation, an aliquot of the supernatant is derivatized. The reaction mixture is analyzed by LC MS/MS on an Agilent 1290/ AB Sciex 5500 system. Peak areas of the respective analyte product ions are measured against the peak area of the corresponding internal standard product ions. Quantitation is performed using a weighted least squares regression analysis generated from fortified calibration standards prepared immediately prior to each run.

We have several **Secondary Outcomes**. For **Specific Aim 3** cardiometabolic profiles will be assessed via assays for high-density lipoprotein cholesterol (HDL-C), triglycerides, fasting insulin/glucose, and c-reactive protein (CRP). All blood assays will be conducted by the *UMN Advanced Research and Diagnostic Laboratory* (see 'Facilities' document). Blood samples collected will be stored at -80°C prior to batch-processing. Resting blood pressure (BP) will be taken using an Omron Automatic BP Cuff (Omron; Lake Forest, IL), with the average of the last two BP measurements reported. These cardiometabolic indices form the foundation of the 'metabolic syndrome',⁵⁹⁻⁶³ and we will form a composite continuous score for cardiometabolic disease risk from HDL-C, fasting glucose, triglycerides, the average of systolic and diastolic BP. Specifically, z-scores for each biomarker will be calculated and the within-participant average across z-scores computed and referred to as *cardiometabolic disease risk (CMDrisk*; the primary dependent variable for Specific Aim 3). This score has been used in epidemiologic, experimental, and clinical studies.^{62,64-67} Individual components will be described in secondary analyses as needed. We will also measure HbA1c using standardized procedures and the blood

MEDICAL PROTOCOL (HRP-590)

PROTOCOL TITLE: Exercise and the Gut Microbiome R21

VERSION DATE: 05/11/2022

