collected. The oral microbiome will be assessed using a widely employed salivary testing technique. Participants will be asked to drool into a 50mL tube until 5mL of saliva is collected. For participants that are having difficulty generating saliva, we will ask those participants chew a small piece of orthodontic wax for 5 minutes and then drool into the 50mL tube. We have experience with this non-invasive assessment⁶⁹, with the assessment taking no longer than 5-10 minutes overall and presenting no greater than minimal risk. Other secondary outcomes are necessary to measure to ensure we can properly control for confounding. Dietary composition will be assessed via 3 phone-based dietary recalls. These recalls will be performed on 2 weekdays and 1 weekend day by trained interviewers. Assessment of diet on multiple days allows us to capture the individual variation in participants' diets.⁷¹ We will use these dietary recalls to develop personalized 3-day meal plan to standardize individual dietary behavior prior to stool sample collection. Although randomization should lead to approximately balanced groups with respect to diet, employing dietary recalls at these time points will allow us to adequately statistically control for participants' dietary changes—changes which, if not controlled, might confound study results.^{70,71} Physical activity will be measured during the duration of the study using the Fitbit Inspire 2 smartwatch. Finally, anthropometric outcomes will include height measured using a Seca stadiometer (Seca; Hamburg, Germany), with weight and body composition measured using the Tanita TBF-300a Body Composition Analyzer (Tokyo, Japan).

To collect blood samples and saliva samples as well as body weight, body fat percentage, and blood pressure, we are proposing to employ the following procedures in the designated settings while following all necessary COVID-19 precautions:

Setting: Baseline, week 4, and week 8 visits will occur in the Epidemiology Clinical Research Center (ECRC). We will follow all UMN, OVPR and ECRC approved guidelines for conducting research during the COVID-19 pandemic.

COVID-19 Screening: Participants will complete the OVPR-approved ECRC COVID-19 phone screener the day prior to their visit. Prior to entering the ECRC, participants will call the study coordinator and complete the screening questionnaire again. Upon entry into the building, study staff will assess the participant's temperature.

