7.0 Sharing of Results with Participants

7.1 **Sharing Results:** Following the conclusion of the study, we will share with each participant their anthropometric (weight, waist circumference) and cardiometabolic data (fasting insulin/glucose, triglycerides, cholesterol levels, and blood pressure) collected during the 2-week run-in visit/baseline fasting visit and following the 4th and 8th weeks. We will share these data in a personalized letter to each participant. Further, we will provide participants with an overall aggregated summary of the study's observations and/or any published manuscripts.

7.2 **Sharing Genetic Results:** N/A

7.2.1 **Disclosure of Results:** N/A

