15.0 Statistical Considerations

15.1 Data Analysis Plan: Chi-square and independent *t*-tests will evaluate baseline group differences as appropriate. Mediation analyses will also be conducted. We outline our analysis plans in Section 15.3. ⁸⁶⁻⁹²

MEDICAL PROTOCOL (HRP-590)

PROTOCOL TITLE: Exercise and the Gut Microbiome R21

VERSION DATE: 05/11/2022

15.2 Power Analysis: Power for Aim 1 is based on analyses using alpha-diversity (Shannon Index) as the primary outcome. Taniguchi et al.⁴⁶, reported a mean \pm SD baseline Shannon Index of 5.7 ± 0.6 which is consistent with preliminary data from gut samples collected by [name] in other recent projects. Given this variance, and with a balanced design of $n=50$ in the experimental and control arms ($N=100$ total), we will have >99% power to detect a 1 unit increase in Shannon Index. Power for Aim 2 is based on changes in serum SCFAs. Our SCFA assays will be performed at Metabolon and our colleagues at Metabolon provided information on mean \pm SD for these outcomes in their lab. They are as follows: acetate= 1806 ± 2500 ng/mL, butyrate= 35 ± 43 ng/mL, and propionate= 50 ± 52 ng/mL. With these distributions, we will have >80% power to detect a difference in SCFA levels between treatment and control groups with a magnitude of at least 50% of 1 SD.

The primary outcome for Aim 3 will be a composite score based on the average of the z-scores for the following 5 biomarkers: HDL-C, fasting glucose, triglycerides, average of systolic and diastolic BP, and waist circumference. The standardized mean \pm SD of this *CMDrisk* z-score in [name] sedentary behavior intervention among 575 participants (Grant #: R01CA198971) is 0 ± 0.7 . This provides 80% power to detect a difference in the *CMDrisk* z-score of 0.4, between intervention and control at the conclusion of the study.

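### CMDrisk, the Aim 3 outcome, has five components in 3.2 and 15.2 but four in 5.2, no listed waist measurement, and no stated direction for HDL-C

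*Combined protocol and SAP*

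**What the plan says.** CMDrisk is a secondary outcome of the trial, the main dependent variable for Aim 3, and the outcome of the mediation models in section 15.3. The protocol describes it in three places.

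- **Section 3.2** lists HDL-C, fasting glucose, triglycerides and mean blood pressure, then continues "and waist circumference. Specifically, z-scores for each biomarker will be calculated and the within-participant average across z-scores computed and referred to as" CMDrisk. That makes five components.
- **Section 5.2** builds the score "from HDL-C, fasting glucose, triglycerides, the average of systolic and diastolic BP. Specifically, z-scores for each biomarker". The list stops at blood pressure, which makes four.
- **Section 15.2** states "The primary outcome for Aim 3 will be a composite score based on the average of the z-scores for the following 5 biomarkers" and names waist circumference as the fifth. It takes an SD of 0.7 from an external study of 575 participants and gives 80% power for a difference of 0.4.

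The measurement lists do not include waist. For the visit, section 5.2 has "The study assessment visit will include a fasting blood draw, blood pressure in triplicate, weight measure and body fat assessment in duplicate", plus saliva. Section 3.2 says "anthropometric outcomes will include height, weight, and body composition". Section 5.2 repeats the anthropometric list with instruments, "with weight and body composition measured using the Tanita TBF-300a Body Composition Analyzer".

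Other sections still mention waist. H3 in section 1.1 gives as examples "blood lipids, fasting insulin/glucose, blood pressure, waist circumference". Section 7.1 promises participants "their anthropometric (weight, waist circumference) and cardiometabolic data". Section 13.1 lists waist measurement among possible sources of embarrassment, and section 19.1 says it will be done in a private room.

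Neither 3.2, 5.2 nor 15.2 says that the HDL-C z-score changes sign before averaging.

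**The concern.** The outcome of Aim 3 is not uniquely defined. An analyst who follows 3.2 or 15.2 needs a waist variable that the listed procedures do not collect. One who follows 5.2 builds a different score, to which the SD and power in 15.2 do not belong. Site staff who read 5.2 and then 19.1 cannot tell whether to measure waist.

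The sign of HDL-C is a second open choice. It is the only component for which a higher value means lower risk. Under the literal averaging rule, an improvement in HDL-C raises a score named for risk. With the component count also open, four versions of the outcome fit the text. The total effect is the denominator of the proportion mediated, so its size and meaning depend on which version is used.

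**Working it through.** **Inputs.** From 15.2: SD 0.7 for five components, difference 0.4. From 10.1 and 15.2: 50 per arm. Alpha and sidedness are not stated for Aim 3; two-sided 0.05 is assumed. Power is from the noncentral t distribution unless noted.

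**1. The plan's own figure.** Standard error = 0.7 × √(2/50) = 0.14, and 0.4/0.14 = 2.86. Power is 80.8% (81.5% by the normal approximation). A one-sided test gives 88.7% by the normal approximation and does not match. The stated 80% is therefore right for the five-component score with a two-sided test.

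**2. Four components, equal correlations.** The average of k unit-variance z-scores with common correlation r has SD = √[(1 + (k − 1)r)/k].

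- Five components: (1 + 4r)/5 = 0.49, so r = 0.3625.
- Four components: SD = √[(1 + 3 × 0.3625)/4] = 0.722.
- Power at 0.4: 78.3%.

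**3. Four components, waist correlation varied.** An SD of 0.7 fixes only the mean of the ten pairwise correlations. If waist has mean correlation w with the other four, the mean correlation among those four is r4 = (10 × 0.3625 − 4w)/6. The documents do not give w; 0.2 to 0.5 is an assumption.

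| w | r4 | Four-component SD | Power at 0.4 |
|---|---|---|---|
| 0.2 | 0.471 | 0.777 | 72.2% |
| 0.5 | 0.271 | 0.673 | 83.7% |

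**4. Direction of HDL-C.** Suppose the other components each improve by 0.4 SD and HDL-C improves by h. The improvement in the average is (0.4(k − 1) + h)/k if HDL-C is reversed and (0.4(k − 1) − h)/k if it is not. With r = 0.3625 in the risk direction, the unreversed score has SD √[(5 + 4r)/25] = 0.508 for five components. For four it is √(4/16) = 0.500, because the positive and negative correlation terms cancel.

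| Components | h (SD) | Effect, reversed / unreversed | Power, reversed / unreversed |
|---|---|---|---|
| 5 | 0 | 0.32 / 0.32 | 61.9% / 87.7% |
| 5 | 0.2 | 0.36 / 0.28 | 72.1% / 77.9% |
| 5 | 0.4 | 0.40 / 0.24 | 80.8% / 64.8% |
| 4 | 0 | 0.30 / 0.30 | 53.8% / 84.4% |
| 4 | 0.2 | 0.35 / 0.25 | 67.0% / 69.7% |
| 4 | 0.4 | 0.40 / 0.20 | 78.3% / 50.8% |

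There is no general loss of power. What changes is meaning: in the four-component score an HDL-C gain of 0.4 SD contributes 0.4/4 = 0.10 towards harm instead of 0.10 towards benefit.

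**5. Was the source score reversed?** If HDL-C had been left unreversed and correlated −0.2 to −0.4 with the other four (assumption), an SD of 0.7 would need 25 × 0.49 = 5 + 12r − 8 × (0.2 to 0.4). That gives a mean correlation among the other four of r = 0.74 to 0.87. Values that high suggest that the source study did reverse HDL-C.

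**The case against.** The case for treating this as minor runs as follows.

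- **The waist mentions look like leftover text.** Revision 3 in the revision history records that waist measures were dropped from the in-person visits. Section 3.1 sends the reader to 5.2 for detailed data collection, and 5.2 has both the visit list without waist and the four-component score. This indicates which version was intended and supports the direction of the fix. It does not reconcile the text in force: 3.2 and 15.2 still define the outcome with waist, and 19.1 still says it will be measured.
- **No loss of power is shown.** This stands. The change under equal correlations is 2.5 points, and the wider range rests on an assumed correlation and lies on both sides of 80%. The point is that the stated figure belongs to another score.
- **Reversing HDL-C is implied.** The score is named for risk, section 3.2 cites sources that have used it, and step 5 suggests a reversed source score. This stands in part. HDL-C direction is an unstated step, not a proven error, but it takes few words to state and should not be left to inference.
- **The definition has another gap.** The protocol does not say which mean and SD are used to form the z-scores. That is true, but it is separate and does not remove the contradiction.
- **CMDrisk is a secondary outcome in an exploratory mediation analysis.** This stands and limits the weight of the point.

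**Conclusion.** The concern holds. The current protocol gives two incompatible definitions of the Aim 3 outcome, and the measurement lists in 3.2 and 5.2 support only the four-component one. The SD of 0.7 and the 80% power in 15.2 therefore describe a score that those lists do not yield. For the four-component score, power at 0.4 is 78.3% under equal correlations, with a range of 72.2% to 83.7% that depends on the assumed waist correlation. These figures take 50 analysed per arm and a two-sided 0.05 test. The direction of HDL-C is unspecified, and applied literally the rule would count an HDL-C gain as added risk. This should be fixed. The consequences are confined to Aim 3.

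**What to change.** Put one definition in 3.2, 5.2 and 15.2: CMDrisk = mean of z(fasting glucose), z(triglycerides), z(mean of SBP and DBP) and −1 × z(HDL-C). It would be sensible to name in the same sentence the mean and SD used for standardising.

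Then:

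- remove waist circumference from 3.2, 15.2 and H3, and from the remaining mentions in 7.1, 13.1 and 19.1;
- change the count of biomarkers in 15.2 from five to four;
- restate the SD and power in 15.2 for the four-component score, either from the source study's data or as a stated assumption with a range.

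The cost is wording in seven places (H3, 3.2, 5.2, 7.1, 13.1, 15.2 and 19.1) and one recalculation. No new participant data are needed. The recalculation needs the four-component SD from the source study or, failing that, a stated assumption.
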